4 STATISTICAL METHODS

4.1 Data Quality Assurance

All tables, figures and data listings to be included in the report will be independently checked for consistency, integrity and in accordance with standard PAREXEL procedures.

4.2 General Presentation Considerations

With protocol version 5.0 as of 17 July 2020, on site assessments were consistently reduced to mitigate risk for subjects to be exposed to COVID19 pandemic. Data will be summarized based on schedule of events planned in protocol version 5.0, while all the data collected will be listed.

4.2.1 Treatment Period, Treatment and Sequence

In this Study, two treatment periods are planned: Treatment Period 1 includes visits from Screening (day -45 to -2) to Visit 6 follow-up (day 36); Treatment Period 2 include visits from Visit 6 Baseline (day -1) to Visit 10 follow-up (day 36).

Two treatments are planned for administration to each subject: NAL ER tablets and Placebo tablets.

Two sequences (arms) are also planned; subjects in sequence 1 will receive active NAL ER tablets followed by crossover Placebo tablets in Treatment Period 2; subjects in sequence 2 will receive Placebo tablets followed by crossover NAL ER tablets in Treatment Period 2.

4.2.2 Relative Study Day

4.2.2.1 Relative Study Day in Treatment Period 1

In Treatment Period 1, Study Day 1 is defined as the date of first investigational medicinal product (IMP) intake occurring on Treatment Period 1.

In Treatment Period 1, other study days are defined relative to the Study Day 1 as follow:

• assessments taken before the Treatment Period 1 first IMP administration:

Relative Study Day = assessment date - Treatment Period 1 first IMP intake date

• assessments on or after the repeat administration:

Relative Study Day = assessment date - Treatment Period 1 first IMP intake date + 1.

As soon as the first IMP intake occurs on Treatment Period 2, then the rules outlined in section 4.2.2.2 will apply.

4.2.2.2 Relative Study Day in Treatment Period 2

In Treatment Period 2, Study Day 1 is defined as the date of first IMP intake occurring on Treatment Period 2.

In Treatment Period 2, other study days are defined relative to the Study Day 1 as follow:

• assessments taken on or after Treatment Period 1 Visit 6 (Follow-up) and before the Treatment Period 2 first IMP intake:

Relative Study Day = assessment date - Treatment Period 2 first IMP intake date

• assessments on or after the repeat administration:

Relative Study Day = assessment date - Treatment Period 2 first IMP intake date + 1.

4.2.2.3 Relative Study Day at Visit 6

In most instances, the baseline visit for Treatment Period 2 will occur on the same calendar day as the Follow-up Visit 6 for Treatment Period 1; in this case, relative Study Day at Visit 6 will be calculated for Treatment Periods 1.

In the instance that baseline visit for Treatment Period 2 will occur on a different calendar day as the Follow-up Visit 6 for Treatment Period 1, then rules outlined in section 4.2.2.1 will apply to Follow-up Visit 6 for Treatment Period 1, while rules outlined in section 4.2.2.2 will apply to baseline visit for Treatment Period 2.

4.2.3 Baseline Definition

Unless otherwise specified, in this Study, two Baselines will apply:

'Study Baseline' coincides with the 'Period 1 Baseline' and is defined as the last available assessment prior to the first Treatment Period 1 IMP intake.

'Period 2 Baseline' is defined as the last available assessment prior to the first Treatment Period 2 IMP intake.

Unless otherwise specified, when this SAP refers generically to baseline and change from baseline, it is to be intended as the study baseline defined in this section.

If not otherwise stated, the primary and key secondary endpoints, as well as secondary and exploratory endpoints, will utilize study baseline for statistical models, descriptive and graphical analysis.

4.2.4 Data Listings

All original and derived parameters will be listed.

Listings will include both scheduled and unscheduled measurements; such measurements will appear in chronological order together with the scheduled time points.

All listings will be sorted by sequence (i.e. Arm 1: NAL-ER + Placebo; Arm 2: Placebo + NAL-ER), subject number and time (visit); actual treatment received at timepoint will always be displayed, as appropriate. Study baselines will be flagged in listings.

Unless otherwise specified, relative study day will be provided for each date, please refer to Section 4.2.2 for derivation of relative study days. Study days relative to Treatment Period 1 will be printed as 'TP1:XX' (where XX stays for a particular study day); similarly, study days relative to Treatment Period 2 will be printed as 'TP2:XX' (where XX stays for a particular study day). In most instances, the Baseline visit for Treatment Period 2 will occur on the same calendar day as the Follow-up Visit 6 for Treatment Period 1; in this case, 'TP1:XX' will be printed.

Unless otherwise specified, listings will be presented based on all screened subjects; Screen Failure subjects will be included as well under 'Screen Failure:'.

4.2.5 Data Summaries

Subject disposition, Demographics, Medical History, Treatment Exposure and Treatment Compliance tables will be summarized by sequence (see definition in section 4.2.1).

In efficacy and safety tables (including concomitant medications), results will be summarized under the actual treatment received (NAL-ER or Placebo) independently whether the NAL-ER (and Placebo) was received in Treatment Period 1 or 2. In other words, summaries will be presented by treatment received.

In most instances, the baseline visit for Treatment Period 2 will occur on the same calendar day as the Follow-up Visit 6 for Treatment Period 1; in any case, Visit 6 results will be used as Follow-up for Treatment Period 1, while the baseline for the Treatment Period 2 will be the study baseline (taking into account baseline definition from section 4.2.3).

Continuous data will be summarized in terms of the number of subjects with non-missing values, mean, standard deviation (SD), median, minimum and maximum, unless otherwise stated.

The following rules will apply to all descriptive statistic displays, where 'd' denotes the decimal places in the original reported value:

- n (number of non-missing observations): 0 decimal places (d.p.)
- Mean: d + 1 d.p.
- SD: d + 2 d.p.
- Median: d + 1 d.p.
- Minimum: d
- Maximum: d
- Statistics in percentage: 1 d.p.
- Confidence Intervals (CIs): d + 1 d.p.
- A maximum of 3 decimal places will be displayed.

All CIs will be reported as 2-sided and will be assessed at α =0.05 significance level unless otherwise stated.

Categorical data will be summarized in terms of the number of subjects providing data at the relevant time point (n), frequency counts and percentages. The denominator for the proportion will be based on the number of subjects who provided non-missing responses to the categorical variable. Any planned collapsing of categories will be detailed in the SAP text and the data displays.

Percentages will be presented to one decimal place. Percentages will not be presented for zero counts. Percentages will be calculated using n as the denominator.

In general, for categorical variables showing multiple possible categories, these will be displayed following the within variable logic criteria; where such a logic criterium does not exist (example: gender, race, AE SOC, AE PT), categories will be displayed by overall descending frequencies.

4.2.6 Figures

In figures, results will be summarized based on the treatment (NAL-ER and Placebo) independently whether the NAL-ER (and Placebo) was received in Treatment Period 1 or 2.

Figures will be produced in black and white.

4.3 Software

All report outputs will be produced using a server-based SAS® version 9.3 or a later version in a secure and validated environment. The REPORT procedure (SAS PROC Report) will be used to produce all tables and listings; SAS/GRAPH will be used to produce all figures.

All report outputs will be provided to the Sponsor in RTF format.

4.4 Study Subjects

4.4.1 Disposition of Subjects

The patient disposition including the date the informed consent was signed, date of randomization, date of last dose and the primary reason for End of Study will be listed.

A by subject listing of violated Inclusion/Exclusion criteria will be presented.

A by subject listing of study visits will be presented.

A clear accounting of the disposition of all subjects who enter the study will be provided, from screening to study completion.

Following disposition summaries will be based on all screened subjects:

- Number of subjects screened for entry into the study;
- Number and percent of subjects randomized;
- Number and percent of the subjects treated (with at least one dose of study medication);
- Number and percent of the subjects included in each analysis set (as defined in section 4.5).

Following disposition summaries will be based on the Safety Analysis Set (see section 4.5 for analysis sets definition):

- Number and percentage of subject's early discontinuing the study treatment (along with reasons and treatment period of the discontinuation) by sequence.
- Number and percentage of subject's who completed both treatment periods in the study.

4.4.2 **Protocol Deviations**

A protocol deviation (PD) is any change, divergence or departure from the study design or procedures of a study protocol. Major PDs are defined as those deviations from the protocol likely to have an impact on the perceived efficacy and/or safety of study treatments.

All PDs will be discussed during a Blinded Data Review Meeting (BDRM) shortly before database lock/ unblinding and addressed with the final classification; as well their overall effect will be evaluated on a subject by subject basis. During the BDRM, all PDs and their possible impacts will be discussed between PAREXEL and the Sponsor and will be assessed as 'Minor' or 'Major'.

The impact of Major PDs on the efficacy and/or safety results will be investigated by assessing the robustness of the study results and conclusions to the choice of analysis set, both including and excluding data potentially affected by Major PDs.

This estimation will be performed at the time of BDRM. Results and population assignments will be summarized in the BDRM report which will be signed off by all relevant scientific experts.

All PDs will be listed by subject in the Safety analysis set as defined in SAP section 4.2.4.

4.5 Analysis Sets

A listing will be presented for inclusion of subjects in each of the below defined analysis sets. In general, if not otherwise specified, all the efficacy analyses, including primary secondary and explorative, will be executed on:

- FAS, as the primary analysis set and
- Completers analysis set for assay sensitivity.

Selected efficacy analyses may be repeated on PPS as an additional robustness analysis.

4.5.1 Safety Analysis Set

The safety population will consist of all randomized subjects who have received at least a single dose of investigational product. The safety population will be used in all safety analyses.

4.5.2 Full Analysis Set

The Full Analysis Set (FAS) will consist of all randomized subjects who have taken at least one dose of study medication and provided study baseline and at least one post-baseline primary efficacy variable assessment during the treatment period. The FAS will be used for the primary efficacy analyses.

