2.2 Secondary Objective(s)

- To evaluate the effect of NAL ER tablets on the mean relative change from baseline in 24hour (combined daytime and nighttime) cough frequency (coughs per hour) at Day 22 (dose: 162 mg BID).
- To evaluate the effect of NAL ER tablets on the mean relative change from baseline in nighttime cough frequency (coughs per hour) at Day 22 (dose: 162 mg BID).
- To evaluate the effect of escalating doses of NAL ER tablets on the mean change from baseline on the Evaluating Respiratory Symptoms (E-RS[™]) diary cough scale (E-RS diary question number 2) by treatment at Days 9, 16, and 22.
- To evaluate the effect of escalating doses of NAL ER tablets on the mean change from baseline in the Cough Severity Numerical Rating Scale by treatment at Days 8, 15, and 21.
- To evaluate the effect of escalating doses of NAL ER tablets on the mean change from baseline in the E-RS diary breathlessness scale (E-RS diary questions 7, 8, 9, 10, and 11) by treatment at Days 9, 16, and 22.
- To evaluate the effect of escalating doses of NAL ER tablets on the mean change from baseline in the 14-item the EXAcerbation of Chronic pulmonary disease Tool (EXACT[®]) version 1.1 e-diary tool total score by treatment at Days 9, 16, and 22.

- To evaluate the effect of escalating doses of NAL ER tablets on the mean change from baseline in the Patient Reported Outcomes Measurement Information System (PROMIS[®]) Item Bank v1.0 Fatigue Short Form 7a scale by treatment at Day 21.
- To evaluate the change in the Clinical Global Impression of Change (CGI-C) over time by treatment measured at Day 21.

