3.2.1 Efficacy Variables

Cough frequency is recorder via a wearable digital cough monitor hookup (24-hour recording) provided by external vendor Vitalograph[®] hereby referred to as 'cough monitor'.

Baseline (pre-treatment) recording of cough frequency will be obtained at Visit 2 (day -1) for Treatment Period 1 and at Visit 6 (day -1) for Treatment Period 2. Period 1 baseline will be taken as the general study baseline as explained in the baseline definition at section 4.2.3 of this SAP.

Cough frequency will also be recorded at Visit 5 (day 21) for Treatment Period 1 and at Visit 9 (day 21) for Treatment Period 2.

Cough frequency will be captured in a 24-hour recording.

External vendor Vitalograph[®] will derive and provide daytime cough frequency at each pertinent visit.

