3.2.1.1 Primary Efficacy Variable

Daytime cough frequency at Day 22 is the primary efficacy variable.

Hourly daytime cough frequency is derived by the external vendor and will be received as a transfer SAS dataset named 'FA' under variable FAORRES when FATEST='Cough average Score at daytime'.

"Daytime" is defined as the time the subject is awake in the 24 hours after the digital cough monitor is applied for use. Events, including sleep, late attachment and device removal, are identifiable in recording via combined assessment of cough monitor algorithms and specially trained cough analysts which will identify these periods from the waveform generated and by the content of the sounds heard. Vitalograph[®] analysts are trained in differentiating sleep periods from the subject being asleep. Consequently, identification of the possible sleep time is done by Vitalograph[®] analysts and will be indicated in the data transfer as date and time of sleep start and end.

Of note:

- If the patient gets up for a short period in the night i.e. use the bathroom or drink a glass of water, this will be counted as sleep time.
- If the patient gets up for a longer period, this will be classed as awake time.
- If two or more periods of sleep exist in a recording the start and end times of each sleep period will be identified.

Statistical Analysis Plan

The following events will be recorded and collected in the data transfer, together with start and end date as appropriate:

| Event Name | Description |
|-----------------------|--|
| Sleep | Sleep Period |
| Device Not Attached | The recording is on, but the device is not attached to the subject |
| Recording Ended Early | Recording duration is shorter than what was expected |
| Flagged Area | An area/period of the recording where there is an issue with the result that this period cannot be analyzed. |

Table 1 – Cough Monitor Events

The Vitalograph[®] data transfer will hold the daytime average coughs per hour based on the following calculation, rounded to two decimal places:

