Daytime cough frequency = ((total cough events for a session not within Sleep, Device Not Attached, Recording Ended Early, Flagged Area event periods) / (recording length in seconds - Sleep, Device Not Attached, Flagged Area event period durations)) x 3600. A session is defined as that 24-hour period when cough recording is taking place for an individual subject. For a session with 'Recording Ended Early', the recording early end datetime will be the end datetime for the session. No events will be collected after the recording early end datetime.

Recording of daytime cough frequency is expected in treatment period 1 at Visit 2 (Study baseline: starting on day -1 and ending at day 1 prior to first IMP intake) and Visit 5 (starting on day 21 and ending on day 22), and in treatment period 2 at Visit 6 (Baseline: starting on day -1 and ending at day 1 prior to first IMP intake) and Visit 9 (starting on day 21 and ending on day 22).

A 24-hour recording is required per protocol at each appropriate visit. All recordings considered valid per Vitalograph[®] quality assessment will be used in analysis, irrespective of actual duration. Cough frequency will be computed based on the actual recording duration.

For the primary endpoint analysis, daytime cough frequency will be log transformed on the natural log scale; ratios will be then calculated per subject per period as log (Visit cough / Study baseline cough) which would represent, upon back transformation and subtraction from 100%, a percent reduction in daytime cough frequency versus study baseline.

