4.11 Efficacy Evaluation

All efficacy summaries and analyses will be based upon the FAS as defined in Section 4.5, unless otherwise specified.

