4.11.3.4 E-RS diary

E-RS breathlessness (items 7, 8, 9, 10, and 11) and cough items (item 2) will be flagged in the EXACT 14-item e-Diary Tool data listing.

Scores obtained at the E-RS breathlessness scales will be summarized by actual treatment received and visit in terms of absolute values and changes from study baseline as defined in SAP section 4.2.3; a ttest will be used to assess statistically significant difference in the changes from study baseline by actual treatment.

A plot showing the absolute mean change from study baseline by actual treatment received will be provided.

4.11.3.5 This secondary analysis will be executed also on the Completers as a sensitivity analysis. Cough Severity Numerical Rating Scale

A by subject listing will be provided for Cough Severity Numerical Rating Scale as defined in SAP section 4.2.4.

Cough Severity Numerical Rating Scale results will be summarized by actual treatment received and visit in terms of absolute values and changes from study baseline as defined in SAP section 4.2.3.

A plot showing the absolute mean change from study baseline by actual treatment received will be provided.

This secondary analysis will be executed also on the Completers as a sensitivity analysis.

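### Entry to the FAS depends on a Day 21–22 cough recording, so Period 1 stoppers' collected NRS (Days 8, 15) and EXACT/E-RS (Days 9, 16) scores are left out of the by-visit results, while Period 2 stoppers' scores are kept

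*SAP*

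**What the plan says.** SAP 4.5.2 requires, besides randomisation and one dose, that the patient "provided study baseline and at least one post-baseline primary efficacy variable assessment during the treatment period". SAP 3.2.1.1 fixes what that variable is: "Daytime cough frequency at Day 22 is the primary efficacy variable". On timing, SAP 3.2.1 states "Cough frequency will also be recorded at Visit 5 (day 21) for Treatment Period 1", with the matching recording at Visit 9 in Period 2. In the schedules of events (protocol Tables 1 and 2, SAP Appendices 1 and 2) the Premature Discontinuation column has no cough recording.

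The set is then applied generally. SAP 4.5 says that "all the efficacy analyses, including primary secondary and explorative, will be executed on" the FAS, with Completers as the sensitivity set, and SAP 4.11 repeats: "All efficacy summaries and analyses will be based upon the FAS as defined in Section 4.5, unless otherwise specified". SAP 4.11.3.3 to 4.11.3.5 name no wider set for EXACT, E-RS or NRS.

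These scores are collected independently of the monitor. The NRS is taken at Days 8, 15 and 21, and EXACT (which contains the E-RS items) every evening. The secondary objectives in SAP 2.2 ask about escalating doses, for instance the mean change from "baseline in the Cough Severity Numerical Rating Scale by treatment at Days 8, 15, and 21", and about EXACT and E-RS at Days 9, 16 and 22. SAP 4.11.3.5 plans that "Cough Severity Numerical Rating Scale results will be summarized by actual treatment received and visit". SAP 4.11.3.3 and 4.11.3.4 plan the same for EXACT and E-RS breathlessness and add a t-test by actual treatment.

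**The concern.** The objectives on escalating doses concern what patients reported at the 54 mg and 108 mg BID steps. A patient who reaches Day 15 of Period 1 and then stops has on-treatment scores for both steps, yet leaves the analysis because a different measurement, due about a week later, was never made. Missing data and imputation are not the issue: the scores exist.

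The rule also works differently in the two periods. Period 1 patients in the intermediate-visit tables have been selected for reaching a Day 22 recording at some point. Period 2 patients have not been selected on how that period went, because their Period 1 recording already qualifies them. Each treatment column pools the two kinds. If stoppers respond less than those who continue, the mean change at the early visits is too favourable. The NAL ER column suffers more than the placebo column if stopping is more common on NAL ER.

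**Working it through.** **1. The plan's own figure.** Protocol 11.1 gives 44 completers, 26% dropout and about 60 randomised. 44 / (1 − 0.26) = 59.5, rounded up to 60, and 60 × 0.74 = 44.4. This reproduces. The planned loss is 60 − 44 = 16 patients.

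**2. Who is in the FAS.** Under protocol 6.3.3 a patient who stops goes to the Premature Discontinuation Visit and then to follow-up; no crossover is described.

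| Patient stops before the period's Day 22 recording | Qualifying recording | In FAS? |
|---|---|---|
| NAL ER, Period 1 (Arm 1) | none | no |
| Placebo, Period 1 (Arm 2) | none | no |
| NAL ER, Period 2 (Arm 2) | Period 1, on placebo | yes, if valid |
| Placebo, Period 2 (Arm 1) | Period 1, on NAL ER | yes, if valid |

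The Completers set (4.5.3) and the optional Per Protocol Set (4.5.4, a subset of Completers) are narrower, so neither recovers the first two rows.

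**3. How many.** If 0, 4, 8, 12 or 16 of the 16 stop before the Period 1 recording, the FAS is 60, 56, 52, 48 or 44. That leaves out 0%, 6.7%, 13.3%, 20.0% or 26.7% of those randomised.

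**4. Effect on the NAL ER mean change at an intermediate visit (illustration).** From the plan: 30 per arm and 26% total dropout. Assumed: per-period stopping proportions pN on NAL ER and pP on placebo, with (1 − pN)(1 − pP) = 0.74; a share f of NAL ER stoppers stop after the visit and so have a score at it; mean change is 1 in stayers and 0 in stoppers.

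- Stayers: S = 30(1 − pN) + 30(1 − pP)(1 − pN)
- Arm 1 stoppers with a score, left out: A1 = 30·f·pN
- Arm 2 stoppers with a score, kept: A2 = 30(1 − pP)·f·pN
- Mean over all measured = S/(S + A1 + A2); FAS mean = S/(S + A2)
- Ratio of FAS mean to measured mean = (S + A1 + A2)/(S + A2)

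Highest case, pN = 0.26, pP = 0, f = 1: S = 22.2 + 22.2 = 44.4 and A1 = A2 = 7.8. The measured mean is 44.4/60 = 0.740, the FAS mean 44.4/52.2 = 0.851, and the ratio 60/52.2 = 1.149.

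Lowest case, pN = pP = 0.14, f = 0.25: S = 25.8 + 22.19 = 47.99, A1 = 1.05, A2 = 0.90. The ratio is 49.94/48.89 = 1.021.

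| Stopping per period | f = 1 | f = 0.5 | f = 0.25 |
|---|---|---|---|
| All on NAL ER (0.26 / 0) | 1.149 | 1.081 | 1.042 |
| NAL ER about twice placebo (0.185 / 0.092) | 1.107 | 1.056 | 1.029 |
| Equal (0.14 / 0.14) | 1.081 | 1.042 | 1.021 |

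The arm size of 30 cancels from the ratio, so a smaller trial with the same proportions gives the same percentages but smaller counts. The table describes the NAL ER column only. With equal stopping, f and response assumptions in both treatments, the placebo column is inflated by the same factor.

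**The case against.** The strongest objection is that the FAS may not be the binding rule. SAP 3.2.1.2.3 to 3.2.1.2.5 define the post-baseline value for the summary tables only as the Day 22 record, or the last one within the 5 days before it. Read literally, an early stopper contributes nothing however wide the set is. This stands as a limit on the fix: changing the set alone is not enough. It does not remove the point, because SAP 2.2 asks for Days 8/15 and 9/16 and SAP 4.11.3.3 to 4.11.3.5 plan summaries by visit. The SAP cannot meet those objectives without using the intermediate values.

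Several stronger readings are tempting, and the documents do not support them:

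- *The rule singles out NAL ER.* It depends on period, not drug; placebo stoppers are treated in mirror image. An imbalance between treatments needs unequal stopping or response, which the documents do not quantify.
- *PROMIS data are lost too.* PROMIS is summarised at Day 21 (SAP 4.11.3.6) and no rule maps the discontinuation visit to that day. That visit may also fall up to two weeks after the decision to stop (protocol 6.3.3), so its score need not be on-treatment.
- *The Day 21/22 results or the primary result are biased by this rule.* With no imputation, most Period 2 stoppers have no Day 22 value either. A patient without any Day 22 cough value cannot contribute to the primary model.
- *The scores are discarded.* They remain in the listings, which cover all screened subjects (SAP 4.2.4).
- *A 15% overstatement is to be expected.* That is the extreme corner of the table. Protocol 6.5 says that treatment-limiting effects occur early, which points to stops before Day 8 and a smaller f.

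It is also fair to say that the NRS has no planned test, that this is a proof-of-concept trial, and that recruitment ended early (SAP 4.14, 4.15), so 60 is a planning figure. The SAP's move from the protocol's Completers set to the FAS already recovers the Period 2 stoppers.

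**Conclusion.** The point holds for the intermediate visits: NRS at Days 8 and 15, and EXACT/E-RS at Days 9 and 16. There the FAS rule leaves collected scores out of summaries, and for EXACT and E-RS breathlessness potentially out of t-tests, according to the period in which the patient stopped. The NAL ER change at the lower dose steps can be overstated by about 2% to 15% under the stated assumptions, and exceeds 10% only when stopping is mostly on NAL ER and all of it comes after the visit. The direction rests on stoppers responding less; if they respond more, it reverses. The actual split and timing of stopping are not in the documents. This is a cheap improvement to secondary, largely descriptive results and does not threaten the primary analysis.

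**What to change.** Keep the present FAS for the cough-frequency endpoints. In SAP 4.5.2 and 4.11, add that NRS, EXACT and E-RS are each analysed in all randomised, dosed patients with a study-baseline value and at least one post-baseline value of that endpoint, whether or not a cough recording exists. Apply the rule identically in both sequences and show n per visit.

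In the same revision, amend SAP 3.2.1.2.3 to 3.2.1.2.5, which now define only a Day 22 record, so that they state how the Day 8 and 15 NRS values and the Day 9 and 16 EXACT/E-RS values are selected for the by-visit tables. Without this second change the first has no clear effect.

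The cost is a few lines of text and one population flag per endpoint, with no new data. The small downside is that n will differ between the cough-frequency and the patient-reported tables.
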